## 7. Investigational Plan

### 7.1. Purpose

The purpose of the pilot reader study is to provide credible performance estimate information to properly plan, design, and power the pivotal reader study with respect to:

- the radiologists' performance metrics for the two reading modalities, i.e., FFDM read on the ASPIRE Bellus II workstation ("FFDM"), and Synthesized (S-View) read in conjunction with DBT on the ASPIRE Bellus II workstation ("DBT plus S-View")
- the magnitude and direction of differences between performance metrics for the two modalities; and
- variance components and correlations that would influence sample sizes and case mix for the pivotal reader study (FMSU2017-002B) comparing performance metrics between the two modalities.

The AUC, sensitivity, specificity, and recall rate are the key performance indices for the study analysis. We are particularly interested in performance in the subgroups of biopsy benign cases and recall cases, as this will influence case mix for the pivotal reader study.

### 7.2. Study Endpoints

All of the following primary, secondary, and additional (optional) endpoints are measured on the FFDM read, DBT plus S-View read, and their difference. All measurements require correct lesion localization.

The **primary endpoint** is:

- Non-inferior per-subject average area under the ROC curve (AUC) for DBT plus S-View versus FFDM, based on per-subject POM scores and requiring correct lesion localization

The **secondary endpoints** are:

- Superior per-subject average AUC for DBT plus S-View versus FFDM
- Non-inferior and/or superior per-subject average recall rate for all non-cancer cases for DBT plus S-View versus FFDM
- Superior per-subject average specificity for DBT plus S-View versus FFDM
- Non-inferior and/or superior per-subject average sensitivity for DBT plus S-View versus FFDM
- Non-inferior per-subject average recall rate for DBT plus S-View versus FFDM for all cancer cases

### 7.3. Pilot Study Population

A minimum of 100 cases will be selected from mammograms that were acquired during Fujifilm protocol FMSU2013-004A.

Images to be used in this study were acquired at image-acquisition sites listed in Table 1. The sites participated in protocol FMSU2013-004A and acquired images of subjects who consented to participate in the study. As part of the consent process, subjects agreed that

image data and supporting documentation could be used for future research and investigations.

### 7.3.1. Case Reference Standard

The **reference standard for a cancer case** is a case in which at least one lesion is confirmed as malignant by biopsy or surgery.

The **reference standard for a non-cancer case** is biopsy or surgery for benign cases, or interpretation by radiologists at the acquisition site for recall and normal cases.

### 7.3.2. Sample Size and Case Mix

Approximately 18 cancer cases and approximately 82 non-cancer cases will be selected by the statistician for this pilot reader study from the library of FFDM and DBT mammograms collected under Fujifilm protocol FMSU2013-004A. All cancer cases will undergo the truthing process described in section 8. The approximately 82 non-cancer cases will include:

- approximately 17 biopsy benign cases,
- approximately 19 recall cases, and
- approximately 46 normal cases.

### 7.3.3. Inclusion and Exclusion Criteria

All cases for this pilot MRMC reader study will meet the following eligibility inclusion and exclusion criteria (see also Appendix B for inclusion and exclusion criteria from protocol FMSU2013-004A). Only subjects who were consented, met all inclusion criteria and none of the exclusion criteria, and completed the needed work-up to establish the ground truth were considered evaluable.

***Inclusion Criteria***

- Eligible subjects under protocol FMSU2013-004A, defined as female subjects with known true clinical status and with complete FFDM and DBT examinations, in which there is sufficient anatomical coverage, sufficient contrast, and no significant motion or other artifacts, as determined by the image-acquisition sites.
- Meet none of the exclusion criteria under protocol FMSU2013-004A.

***Exclusion Criteria***

- Subjects who are in violation of protocol FMSU2013-004A.
- Subjects who meet exclusion criteria under Fujifilm protocol FMSU2013-004A.
- Subjects with unknown clinical status.
- Any subject whose positive mammogram was not read during the truthing process (see section 8) will not be considered for the pilot reader study.

**7.3.4. Case selection and Targeted Distribution**

Cases selected for this study were those that the statistician selected for FMSU2013-004E and FMSU2013-004F, with the replacement of those cases lost to follow-up or otherwise not available for this pilot reader study. Within each category of cancer, benign, recall, and normal, cases will be randomly selected to provide the (targeted) representative distributions of:

- mammographic finding types (Table 2),
- breast composition (Table 3),
- and equal distribution across acquisition site, to the extent that this can be accomplished using cases in the FMSU2013-004A case library.

**Table 2.Targeted distribution of mammographic finding types (approximation)**

Case Type	Calcification	Mass	Total
Cancer	8	10	18
Benign biopsy	7	10	17
Recall	3	16	19
Normal	0	0	46
Total	28	31	100

**Table 3.Targeted distribution of mammography breast composition (approximation)**

Breast Tissue Density	BI-RADS Breast Tissue Composition Category	Total
Fatty (50%)	a - Almost entirely fatty	10% to 15%
	b - Scattered areas of fibroglandular density	40% to 45%
Dense (50%)	c - Heterogeneously dense	35% to 40%
	d - Homogeneously dense	5% to 10%
	Total	100%

#### **7.4 Risk/Benefit Assessment**

The probable benefits of the device are based on the data that will be collected in the clinical study being conducted to support PMA supplement approval.

The ASPIRE Cristalle DBT System is used to reconstruct the breast volume from limited angle projections while eliminating the tissue overlapping effects observed in FFDM projections. It is likely to benefit a substantial number of screening patients whose cancers could have otherwise been missed due to tissue superimposition (false negatives), or who may otherwise have been unnecessarily referred for additional workup (false positive).

Synthesized view (S-View) images are created from the reconstructed DBT images. Without the need of additional radiation exposure to the patient, the S-View image is generated by “combining” the DBT images of that view into a single 2D synthetic mammography image.

The device has no significant risk of direct harm to the patient.

The primary risk of the device comes from the possibility of false positive and false negative clinical decisions when using the images produced by the ASPIRE Cristalle DBT System. Fujifilm has designed an MRMC study to compare the performance of readers with FFDM alone and with DBT plus S-View. The study design is consistent with other mammography studies. Because MRMC studies are conducted outside the clinical setting, with an enriched case set, and without patient history, the generalizability of some figures of merit such as recall rate, sensitivity, and specificity is limited. The design is considered acceptable in order to reduce the size of the trial and avoid confounders.

## 8. The Truthing Process

### 8.1. Purpose

The purpose of the truthing process will be to determine, for the cancer cases selected by the statistician for this pilot reader study, the type of lesion (or finding) visible within the mammogram, the location for each lesion (or finding), and the pathology results.

### 8.2. Qualification Criteria and Training for the Truther

The truther is a radiologist who meets the expert radiologist eligibility criteria (below), is not associated with the diagnosing of cases at the image-acquisition sites (under Fujifilm protocol FMSU2013-004A), will not be associated with the reading of images in this pilot reader study, and will be available to perform the responsibilities as the study truther and conduct the truthing process.

**Base qualification criteria:** The base criteria for the truther are as follows:

- Board-certified radiologist.
- MQSA qualified for both FFDM and tomosynthesis
- Experience reading FFDM images on a monitor (softcopy).
- Experience reading DBT images on a monitor (softcopy).

In addition, to merit the designation “expert in breast imaging,” the radiologist selected to be the study truther must meet one or more of the following criteria:

- Have instructed breast imaging in a professional society meeting.
- Have authored textbooks, book chapters, or peer-reviewed journal articles in mammography.
- Have interpreted mammography for at least 10 years.

**Training:** The truther will participate in a training session to ensure understanding of the ASPIRE Bellus II workstation, reading DBT plus S-View images, the protocol, the eCRFs, study processes, GCP, and the obligations entailed by study participation. Particular attention will be given to reviewing the annotation process.

The study truther will be available as necessary to assist in the conduct of the pilot reader study. Possible services to be provided by the study truther include the following:

- Conduct of the truthing process (see section 8.3) for this clinical study.
- Review of some or all cases selected to be read during a pilot reader study.
- Assistance with any clinical questions pertaining to the clinical investigation.
- Designation of the location and view(s) in which a finding or findings is/are located. The type of lesion (finding) visible within the mammogram and location(s) designated and annotated by the truther will be considered as establishing the true type and location of the finding(s).

### 8.3. Conduct of the Truthing Process

#### 8.3.1. Core Reading Center

Truthing will take place at FUJIFILM Medical Systems, U.S.A., Inc. in Stamford, CT.

### **8.3.2 Preparation of Cases for Truthing**

The study truther may have access to basic information about the subjects including age at exam, brief pertinent medical history, BI-RADS descriptors, finding location, and final clinical assessment. The anonymity of participating subjects will be maintained. See section 12.6.1 for detail about maintenance of subject confidentiality, study ID numbers, and tracking.

Truthing will be performed in a controlled environment with consistent lighting. Using the ASPIRE Bellus II workstation, the truther will respectively review the FFDM and DBT plus S-View images. During the review, the truther will be permitted to use standard softcopy imaging tools and all routine post-processing capabilities (for example, magnification and windowing/leveling).

### **8.3.3 Workflow for the Truthing Process**

The truther will review all cancer cases selected for inclusion in the reader study. The truther will complete an eCRF for each case, based on materials from the image acquisition site including mammograms. For each cancer case the truther will review the images and identify, confirm, and annotate (including the lesion locations and slice, if applicable) for each malignant lesion:

- The type of lesion visible within the mammogram (mass, microcalcifications asymmetric density and/or focal asymmetry)
- The breast, view, and if possible the coordinates and slice, if applicable, in which each lesion is located
- Document the characteristics of the lesion on the eCRF

## 9. Reader Selection and Training

### 9.1. Purpose

The purpose of the training process is to ensure that each reader selected for the reading session has been adequately trained to read and interpret the DBT plus S-View images on the ASPIRE Bellus II workstation. A radiologist with expertise in digital breast tomosynthesis will conduct the training of the radiologists.

### 9.2. Selection and Qualification Criteria for Readers

This study will be conducted with radiologists of varying experience levels, from both community and academic practices, some of whom have limited experience reading 2D synthetic images. These radiologists will not be associated with the acquisition or review of cases and did not participate in the truthing process.

**Base qualification criteria:** All readers must meet the following base criteria:

- Are board-certified
- Are MQSA qualified for both FFDM and DBT interpretation

### 9.3. Conduct of the Training Process

The radiologists will receive approximately two hours of training in the evaluation of DBT plus S-View images to familiarize them with the S-View images. Training will consist of the trainer presenting a brief didactic lecture explaining how synthetic 2D images are generated and the differences, advantages and pitfalls compared with digital mammography. The trainer will demonstrate how to use and interpret S-View images by presenting selected cases to demonstrate the range of typical anatomy, breast density and abnormalities identified with DBT. Training will also consist of a hands-on session at the workstation to provide the readers with an overview of its DBT-specific functionality. For each view, mediolateral oblique (MLO) and cranio-caudal (CC), 2D FFDM and the complimentary S-View image for the same view will be shown with the DBT images. The training will also emphasize that the S-View images alone will not be used for diagnosis, and scoring will be based on the appearance of the lesion on the DBT images.

### 9.4 Conduct of the Reading Process

#### 9.4.1 Purpose and Conduct

The purpose of the reading process is for the readers to provide the BI-RADS assessment categories, probability of malignancy (POM) scores, recall scores, locations and types of any finding(s) on the eCRFs for their interpretation of the study cases; with FFDM images and DBT plus S-View images on the ASPIRE Bellus II workstation.

Following the successful completion of the reader training, the readers will independently review and score each of the image sets of the reader study case set. Each reader will work at a designated workstation and will independently perform two reads on all cases. Each reader will read each case both as a FFDM read, and a DBT plus S-View read on the ASPIRE Bellus II workstation. Each reader will read half the cases on FFDM and the other half of the cases on DBT plus S-View during the first visit. The reader will then read the complimentary FFDM and DBT plus S-View during the second visit. In order to minimize memory recall bias, the two reading visits will be separated by a memory washout period of approximately four weeks.

Interpretation of mammography images will be performed in a controlled environment with consistent lighting. The review workstations will be preloaded with the cases. The readers will be permitted to use standard softcopy imaging tools, and all routine post processing capabilities (e.g., magnification, windowing and leveling) will be permitted. Hotkeys will be provided on the workstations for consistency and accuracy of the reading process. The reading time allowed per case will not be limited. A lunch break will be offered during each reading session, and radiologists will be encouraged to take a 5-10 minute break each hour, as needed. Each reader will dictate their interpretations to a trained scribe, who will enter the dictation directly into the eCRF. Each reader will sign an attestation form verifying the documented information.

#### **9.4.2 Core Reading Center**

The reading process with 6 radiologists selected for the pilot reader study will be conducted at International HealthCare, LLC in Norwalk, CT.

#### **9.4.3 Preparation of Cases for Interpretation**

To maintain subject confidentiality, no identifying patient data will be displayed. Unique image identifiers associated with the case ID number will be visible in each DICOM header for tracking purposes. To maintain reader confidentiality, a unique ID number will be assigned to each radiologist participating in the pilot reader study for entry on the eCRFs.

#### **9.4.4 Workflow for the Interpretation of Cases**

The readers will be told that the samples of cases do not represent a standard screening population, and will be blinded to the actual distribution and nature of the set of images they will be asked to review. Readers will be masked to the reference standard and image acquisition interpretations (under protocol FMSU2013-004A) for each case. Readers will not have access to prior mammograms or other clinical information. All readers will perform their interpretations independently.

Each study reader will be randomly assigned to a unique case block (approximately 50% of the study cases per block) combination reading order. All study readers will ultimately interpret all study cases in both FFDM, and DBT plus S-View formats. Readers will interpret

the preloaded mammograms in their assigned randomized order with the use of barcode scanner/barcodes.

**General instructions** for the readers are as follows:

- Do not record single punctuate or round calcifications and vascular calcifications, given the high prevalence of these benign findings and their low probability of cancer.
- Consider all views available from both breasts to determine if you would recall the case.
- For examinations with multiple findings, record the types and locations of all findings in the eCRF and/or a breast schematic diagram that divides each breast image into sections and image slice for DBT images. Record the finding locations beginning with the most suspicious lesion (up to three lesions per case).
- Provide a BI-RADS assessment category in 1 through 5 for each annotated finding.
- Provide a probability of malignancy (POM) for each annotated finding according to the guidance listed in Table 4 (below).

**Probability of Malignancy (POM):** POM is a 0 to 100 score assigned by readers to each suspicious finding, as their perception of the percentage chance that the suspicious finding might be malignant. To help the assignment of POM scores readers will be instructed to use the entire POM scale, with descriptions of POM values provided in Table 4 only as guidance:

**Note:** POM scores will be determined and analyzed separately from the BI-RADS assessment category.

**Table 4. Probability of malignancy (POM) guidance**

POM Score (%)	Description
0-20	Negative/Benign
21-40	Probably benign
41-60	Possibly malignant
61-80	Probably malignant
81-100	Malignant

**Interpretation instructions** for the readers are as follows:

The reader will complete the eCRFs for each case for the two reads. For each case on each read, the reader will first record whether there are mammographic findings. If the answer to this question is “no” the reader will be asked to confirm for this case: a BI-RADS assessment

category of 1 or 2, a POM score following the POM guidance provided in Table 4, and recall decision of “no”. If the reader answers “yes” to whether there are mammographic findings, the reader will be asked to confirm an initial BI-RADS assessment category of 0, and will then provide detailed information on each suspicious finding:

- Affected breast (right or left)
- Type (includes mass, asymmetry, and/or architectural distortion), microcalcifications, or mass with microcalcifications, or other
- “Forced” BI-RADS assessment category 1, 2, 3, 4, or 5
- POM score 0 through 100
- The reader will then be asked whether the case shall be recalled (“yes” or “no”), their forced BI-RADS assessment category (1, 2, 3, 4 or 5), and POM score 0 through 100.

A study scribe representing the sponsor will capture the radiologist’s results on the eCRFs to ensure completeness.

In cases with mammographic findings, consistency of POM scores with BI-RADS assessment categories and recall decisions will not be forced – i.e. readers will be permitted to use the full range of POM scores for a finding (following the POM guidance provided in Table 4) no matter what BI-RADS assessment category they assign to it.

#### **9.4.5 Reading Sessions with a Memory Washout Period**

Each reader will read each case both as an FFDM read and a DBT plus S-View read, on the ASPIRE Bellus II workstation. Each reader will read half the cases on FFDM and the other half of the cases on DBT plus S-View during one visit. The reader will then read the complementary FFDM and DBT plus S-View exams during the second visit. In order to minimize memory recall bias, the two reading visits will be separated by a memory washout period of approximately four weeks.

##### **Reading Session Order**

- a. 100 cases which were used in prior Fujifilm pilot studies were selected, with some updates made due to subjects that did complete the study per protocol, etc. The randomization was updated to reflect the replacement cases, and for a change in workstation capabilities that will allow use of a worklist rather than requiring cases to be loaded on each reader’s workstation in her or his assigned interpretation order.
  - i. Group A – case number 101 through 200
  - ii. Group B – case number 201 through 300
- b. Sessions format:

Session 1		Session 2	
Cases	Sequence #	Cases	Sequence #
Group A FFDM cases	1501 - 1550	Group A DBT plus S-View cases	2501 - 2550
Group B DBT plus S-View cases	2551 - 2600	Group B FFDM cases	1551 - 1600

- c. Reading order within each group will be randomly determined in the beginning and will be set for the duration of the reader study.
- d. Each session has 100 cases that will be read – 50 FFDM cases and 50 DBT plus S-View cases.
- e. Reading format:

Reader	Day 1 Read		Day 31 Read	
	Session #	Sequence #	Session #	Sequence #
Reader #1	1	1501-1600	2	2501-2600
Reader #2	1	1501-1600	2	2501-2600
Reader #3	1	1501-1600	2	2501-2600
Reader #4	1	1501-1600	2	2501-2600
Reader #5	1	1501-1600	2	2501-2600
Reader #6	1	1501-1600	2	2501-2600

## 10. The Lesion Matching Process

### 10.1 Purpose

The purpose of the lesion matching process will be to determine if the location and type of a finding identified by the reader match those of a malignant lesion annotated by the truthe, i.e., correct lesion localization and type.

### 10.2 Qualification Criteria and Training for the Lesion Matcher

An expert not associated with diagnosing cases at the image-acquisition sites or serving as a reader interpreting images on this pilot reader study will serve as the lesion matcher for this study. This expert may be an experienced, MQSA qualified mammography technologist with an active license, or a board-certified radiologist that is MQSA qualified for both FFDM and tomosynthesis; if the latter, this expert radiologist may be the same person as the truthe.

**Base qualification criteria:** The base criteria for the lesion matcher are as follows:

- Has an active license as a breast mammogram technologist
- Has experience with clinical research in the GCP environment
- Or, Study truthe (refer to truthe qualifications in section 8.2)

**Training:** The lesion matcher will participate in a training session to ensure understanding of the ASPIRE Bellus workstation, the protocol, the eCRFs, study processes, GCP, and the obligations entailed by study participation. Particular attention will be given to the lesion matching process.

### 10.3 Conduct of the Lesion Matching Process

#### 10.3.1 Core Matching Center

Lesion matching will take place remotely, with results documented within the truthe/lesion matching database.

#### 10.3.2 Preparation of Cases for Lesion Matching

The lesion matcher will have access to both the reader's eCRF and the truthe's eCRF. The eCRF and images contain the annotated information, such as case ID number, the finding location(s), and finding type(s) which are required for the determination of correct lesion localization. The matching is limited to cases with malignant lesions. For each case with cancer, the lesion matcher determines if the annotation by the reader matches with that made by the truthe.

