#### 10.3.3 Workflow for the Lesion Matching Process

The lesion matching process is limited to those cases with **malignant lesions**. Based on the case ID number on the truthe's eCRF, the lesion matcher identifies the reader's eCRF with the same case ID number. The lesion matcher compares the finding location(s) and finding type(s) of the reader's eCRF and annotated images to those of the truthe's eCRF, to

determine if the reader made the correct lesion localization. The process will be repeated for each reader's eCRFs that have the same case ID number as the truther's eCRFs, and for every reader. The lesion matcher will record the lesion matching results on the eCRFs.

- For each truther's eCRF, identify and confirm the corresponding reader's eCRF that contains the same case ID number
- Identify and match the location (breast, view, and if possible the section and/or slice) and type of finding(s) with those of the truther's eCRF
- Document the matching results on the eCRF

Note: To allow for the possibility of lesions located on breast section boundaries, the reader will get credit for correctly locating a lesion if the matcher determines that the annotations match even if an adjacent quadrant is recorded on the case report form. In this situation, we anticipate x/y coordinates to be within 2 centimeters and slice numbers to be within 10 slices. Readers will not get credit for correctly locating a lesion if the matcher determines that the annotations do not match, even if the same quadrant is recorded on the case report form; in this situation the x/y coordinates and/or slice numbers also usually would not match with the pre-specified tolerance. The lesion matching process will be supported by programmatic (computer) determination of whether x and y coordinates are within 2 centimeters; and whether slice numbers are within 10 slices.

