## LESION #1

4. Affected breast:  Right  Left

5. What is the most suspicious finding type? (check all that apply):

a.  Mass

[figure not shown]
b.  Asymmetry

c.  Calcification

d.  Architectural Distortion

e.  Other (please specify):

6 - 9. Mark an X at the location(s) of the lesion on the Mammogram:

6.

7.

8.

9.

10. Lesion Location: N/A  CC: X   Y   Slice (DBT Only)

N/A  MLO: X   Y   Slice (DBT Only)

11. Based on the images reviewed, what is your forced BI-RADS score for this lesion? (check one)

1

2

3

4

5

12. What is your estimated probability of malignancy for this lesion (0-100%)?

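### The plan does not hide POM, BI-RADS and recall entries from the lesion matcher, whose judgement decides whether a cancer read with findings keeps its score

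*Protocol*

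**What the plan says.** **Access.** Protocol 10.3.2 says "The lesion matcher will have access to both" the reader's eCRF and the truther's. It gives examples of what the forms and images contain: case ID, finding locations and "finding type(s) which are required for the determination of correct lesion localization". It does not restrict the matcher to those items.

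**What the reader's form holds.** In SAP Appendix 1, each lesion page of the Reader Study Form carries type and coordinates. On the same page, item 11 asks "Based on the images reviewed, what is your forced BI-RADS score for this lesion" and item 12 asks for that lesion's POM. The last page holds the overall recall decision, BI-RADS and POM.

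**Who decides.** Under protocol 10.3.3, "The lesion matcher compares the finding location(s) and finding type(s) of the reader's eCRF and annotated images" with the truther's record. For lesions at section boundaries, "the reader will get credit for correctly locating a lesion if the matcher determines that the annotations match", even when the recorded quadrant is an adjacent one. Conversely, "Readers will not get credit for correctly locating a lesion if the matcher determines that the annotations do not match", even when the quadrant agrees. A computed check of 2 cm in x/y and 10 slices supports this judgement but does not replace it. SAP 3.5 does not mention the check.

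**Masking.** SAP 3.6 masks the readers. SAP 4 says the statistician is not blinded to reading condition. Neither document masks the matcher, and the Lesion Matching Form records the image type.

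**Consequence of no match.** Under SAP Tables 1 and 2, a cancer read with findings but no match gets POM 0 (or the reader's lowest POM in that modality) and BI-RADS 1, and a recall becomes no recall.

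**The concern.** Matching is defined on location and type (protocol 10.1 and 10.3.3), so the reader's scores should play no part in it. As written, the person who settles a borderline mark may have in view how suspicious the reader thought it was. A mark scored POM 90 and BI-RADS 5 may be credited more readily than one at the same distance scored POM 25 and BI-RADS 3. The derived score would then depend partly on itself.

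The step feeds the primary AUC, sensitivity and the cancer recall rate. Score-led matching would affect each modality's estimates. It would also affect the difference if one modality draws higher scores or produces more borderline marks, even if the matcher has no preference between modalities. SAP 4.10 takes the AUC difference, variance components and correlations from this pilot to size the pivotal study.

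**Working it through.** The plan states no figure that depends on masking the matcher, so there is none to reproduce. The check is how far one matching decision moves the endpoints.

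**Inputs from the documents**
- 18 cancer and 82 non-cancer cases (SAP 2.1). The mix adds up: 17 + 19 + 46 = 82 and 18 + 82 = 100.
- 6 readers, all reading every case in both modalities (SAP 2).
- Margins: 0.05 for AUC (SAP 4.6.1); 0.10 for sensitivity and for cancer recall (SAP 4.6.2).

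**Reads at stake.** 18 × 6 = 108 cancer reads per modality, 216 in all. Only those with recorded findings and a borderline mark are exposed. A cancer read with no findings keeps the reader's own scores.

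**AUC.** Let c be the share of non-cancer cases ranked below the matched POM (ties count half), and f the share of non-cancer cases at the floor score. In the trapezoidal AUC, a matched read contributes c/18 to its reader's AUC and a reset read contributes (f/2)/18. One changed decision therefore moves:
- that reader's AUC by (c − f/2)/18, at most 1/18 = 0.056;
- the six-reader average by (c − f/2)/108, at most 1/108 = 0.0093.

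Neither c nor f is in the documents. I assume c from 0.7 to 1.0. A matched POM above the floor ranks above every non-cancer case at the floor, so f cannot exceed c.

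| c | f | Shift in average AUC per decision | Decisions to reach 0.05 |
|---|---|---|---|
| 1.0 | 0 | 0.0093 | 5.4, so 6 |
| 0.9 | 0.5 | 0.0060 | 8.3, so 9 |
| 0.7 | 0.5 | 0.0042 | 12 |
| 0.7 | 0.7 | 0.0032 | 15.4, so 16 |

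So 6 to 16 changes in the same direction within one modality, or 6/108 = 5.6% to 16/108 = 14.8% of its cancer reads, would move the AUC difference by the whole margin.

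**Sensitivity and cancer recall.** One changed decision moves the average by 1/108 = 0.0093 if the mark was BI-RADS 4 or 5 (or the case was recalled), and otherwise by nothing. 0.10 × 108 = 10.8, so at least 11 changes are needed.

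**Effect on the difference.** With k1 and k2 same-direction changes in FFDM and DBT plus S-View, and per-decision shifts d1 and d2, the AUC difference moves by k2·d2 − k1·d1. This is zero when the counts and shifts are equal. It is not zero when scores or borderline marks differ by modality.

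**The case against.** **Score visibility is inferred.** No sentence says the matcher sees POM or BI-RADS. Protocol 12.5.1 mentions eDC user privilege levels, and a view without scores may exist in practice. This stands as a limit, and a reader should not infer that exposure is established. But the privilege-level remark sets no restriction on the matcher, and the plan as written allows full access.

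**The room for influence is narrow.** Matching has defined criteria, a numerical tolerance, a computed check and a trained matcher who is independent of the sites and readers. This also stands: clear hits and clear misses should not be affected. Borderline marks still rest on judgement, and no computed rule is given for finding type.

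**Equal influence would largely cancel.** A reader might infer that any score-led matching biases the comparison. It does not if it acts alike in both modalities. Within-modality AUC and sensitivity would still be affected.

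**Hiding scores does not hide modality.** Correct. The matcher compares annotated images, slice exists only for DBT, and the matching form states the image type. The safeguard removes the score route only.

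**Six decisions is an extreme figure.** Reaching the AUC margin with six changes needs nearly every non-cancer case ranked below the matched mark and few or none at the floor. With 46 normals among 82 non-cancer cases, ties at the floor are likely. Six is the low end of a range.

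**It is a pilot.** SAP 1 says the results are not meant as a basis for FDA approval, and SAP 4.6.2 calls the secondary endpoints exploratory. The harm is to planning estimates. The forms are headed FMSU2017-002A/B, so the same process may carry into the pivotal study.

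**Conclusion.** The concern holds as a missing safeguard, not as a demonstrated bias. The plan gives the matcher the reader's eCRF without field limits, masks no one but the readers, and lets the matcher's judgement override the computed check. A subjective decision that sets cancer scores is thus open to influence from the scores themselves.

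The size is at most 0.0093 in average AUC per changed decision. About 6 to 16 one-directional changes in one modality would equal the 0.05 margin, and at least 11 would equal the 0.10 sensitivity margin. The AUC range rests on my assumed c and f; the sensitivity count assumes every changed mark was BI-RADS 4 or 5. The number of borderline matches is not given, so the documents do not show that changes on this scale would occur. The change is worth making before matching starts because it is nearly free and removes nothing that matching needs.

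**What to change.** In protocol 10.3.2 and 10.3.3 and in SAP 3.5:

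1. Give the matcher an extract limited to case ID, a coded sequence number, breast, view, section, coordinates, slice, finding type and the annotated images. State that POM, BI-RADS and recall entries are hidden.
2. Have the matcher record a reason whenever the decision departs from the computed check. The comments item on the Lesion Matching Form could hold it.
3. Report agreement between the matcher and the computed check by modality.

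If a sensitivity AUC analysis on the computed result is added, it should not use the check as it stands. The check adds a slice condition that only DBT can have, ignores finding type, and cannot be run where coordinates are N/A (SAP 3.4) or the truther could not give them (protocol 8.3.3). Use the same x/y-only rule in both modalities, keep the type requirement, and fall back to the matcher's decision where coordinates are N/A.

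The cost is slight data-management set-up and, if chosen, one extra analysis run. No new reads or staff are needed. Modality will remain visible to the matcher.
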